- e. Most recent serological findings such as: antiphospholipid antibody tests (anticardiolipin, anti-beta 2 glycoprotein 1 [GP1] and lupus anticoagulant), antiC1q, low-complement (C3/C4), positive anti-double-stranded deoxyribonucleic acid (anti-dsDNA) (IU/mL), anti-U1-RNP, anti-Sm antibody, anti-Rib, and anti-Scl-70

- f. Renal assessments, such as urinary protein to creatinine ratio (UPCR) or 24-hour proteinuria (mg/24-hr) or urine sediment (activity), serum creatinine (mg/dL), and estimated glomerular filtration rate (eGFR) or measured glomerular filtration rate (GFR) (if eGFR is not available) with date of assessment

8) Active non-renal clinical manifestations of SLE (such as mucocutaneous, central nervous system, constitutional, cardiopulmonary, gastrointestinal, hematologic, musculoskeletal, and vasculitis)

- a. Type and date of resolution, if applicable

9) Most recent total Systemic Lupus Erythematosus Disease Activity Index (SLEDAI), such as SLEDAI or SLEDAI-2K ([16](#)), [Appendix 2](#)

10) Renal remission: defined as proteinuria of  $<0.7$  g/d or  $<0.5$  g/d or at physicians' discretion

11) Renal biopsy:

- a. Activity index
- b. Chronicity index
- c. Number of glomeruli

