**Prospective data collection from enrolment (0, 3, 6, 9, 12 months)**

Variables include but are not limited to ([Appendix 1](#)):

- 1) Non-renal and renal clinical manifestations at period start with clinical improvement/worsening assessment at period end
- 2) Changes in disease activity assessment tools used (such as SLEDAI-2K)
- 3) Refractory SLE: defined as inefficacy of cyclophosphamide, use of rituximab, splenectomy, or inefficacy of  $\geq 2$  immunosuppressives (methotrexate, leflunomide, abatacept, anti-TNF, azathioprine, mycophenolate mofetil, and/or mycophenolic acid)
- 4) Renal remission: defined as proteinuria of  $<0.7$  g/d or  $<0.5$  g/d or at physician discretion
- 5) Renal biopsy:
  - a. Activity index
  - b. Chronicity index
  - c. Number of glomeruli
- 6) Changes linked to the primary treatment of the disease:
  - a. Adjustment of the dose by 20% or more, and
  - b. Change happening for longer than 1 month, or
  - c. Change or addition in the type or group of medication (immunosuppressants, biologics, anti-malarial, and steroids)
- 7) Laboratory tests:
  - a. Haematology: white blood cell count ( $\times 10^9/L$ ), haemoglobin (g/dL), platelet count ( $\times 10^9/L$ ), erythrocyte sedimentation rate (mm/hour), C-reactive protein (mg/L)
  - b. Liver function tests
  - c. Lipid profile
  - d. Plasma albumin

- e. Most recent serological findings such as: antiphospholipid antibody tests (anticardiolipin, GP1 and lupus anticoagulant), antiC1q, low-complement (C3/C4), positive anti-dsDNA (IU/mL), anti-U1-RNP, anti-Sm antibody, anti-Rib, and anti-Scl-70
- f. Renal assessments, such as UPCR or 24-hour proteinuria (mg/24-hr) or urine sediment (activity), serum creatinine (mg/dL), and eGFR or measured GFR (if eGFR is not available) with date of assessment

8) HCRU (number of laboratory tests, number of dialyses and use of imaging techniques, ICU hospitalisations/hospitalisations, outpatient visits)

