### 3.3. Study Population

Study participants are patients with lupus nephritis as defined by physician per patient hospital records prior to the enrolment visit or at diagnosis. Retrospective data of patients with diagnosed LN who made at least one centre visit during 12 months prior to the enrolment visit or at diagnosis of LN who fulfil inclusion/exclusion criteria will be abstracted from chart records. The data will be consecutively extracted from paper or electronic records were available. Based on our sample size assumptions and power calculations the study population will aim to recruit 50% of patients with renal remission and 50% of patients with no renal remission at the time of enrolment.

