#### 4.4.3. Secondary Analysis

The first secondary objective is to describe refractory LN cases, involving rituximab, and to assess changes in serological markers of disease activity (including anti-nuclear antibody, anti-dsDNA antibody and complement levels) over the treatment period. This will be achieved by first using summary statistics as per the general consideration of data analysis section at each time point. To assess one-year changes in numeric variables, the paired t-test or Wilcoxon signed rank test will be used while the McNemar's test will be used for changes in categorical variables. In addition, repeated measures analysis will be used to look at changes over the whole time period.

The second secondary objective is to assess the association between clinical factors (disease activity), biomarkers (inflammatory markers and hematological markers), treatment (type and duration of therapy) and renal remission. The variables included in the model will be taken from the measures closest to the time of enrolment. For continuous variables, the nonparametric Wilcoxon test will be used for assessing differences between the patients who attained renal remission versus patients who did not attain renal remission, while the chi-square test will be used for dichotomized variables. Statistically significant factors will be included in the multivariate logistic regression models with renal remission as the dependent variable. Odds ratio and corresponding 95% confidence intervals (CIs) will be presented.

The third secondary objective is to assess impact of LN on HRQoL over a one-year period after diagnosis or enrolment. This will be achieved by looking at changes in the SF-36 physical and mental components, and the total score at one year using the paired t-test or Wilcoxon signed rank test for non-normal distribution. Changes over all the time period will be assessed using repeated measures analysis.

The fourth secondary objective is to estimate HCRU and direct medical cost, associated with LN management across 5 Gulf countries over a one-year period. This will be carried out as per [Section 4.5. Cost Evaluation](#). Generating an estimate for the average HCRU and direct medical cost and creating the 95% CIs for those will be carried out for each country.

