## 11. APPENDIX 2: SYSTEMIC LUPUS ERYTHEMATOSUS DISEASE ACTIVITY INDEX 2000 (SLEDAI-2K)

Name/ID: \_\_\_\_\_ Date of Birth: \_\_\_\_\_ Date of Assessment: \_\_\_\_\_

(Circle in "SLEDAI Score" column if descriptor is present at the time of the visit or in the preceding 10 days.)

SLEDAI Score	Descriptor	Definition
8	Seizure	Recent onset. Exclude metabolic, infectious, or drug causes.
8	Psychosis	Altered ability to function in normal activity due to severe disturbance in the perception of reality. Include hallucinations, incoherence, marked loose associations, impoverished thought content, marked illogical thinking, and bizarre, disorganized, or catatonic behavior. Exclude uremia and drug causes.
8	Organic brain syndrome	Altered mental function with impaired orientation, memory, or other intellectual function (with rapid onset and fluctuating clinical features), inability to sustain attention to environment, and at least two (2) of the following: perceptual disturbance, incoherent speech, insomnia or daytime drowsiness, and increased or decreased psychomotor activity. Exclude metabolic, infectious, or drug causes.
8	Visual disturbance	Retinal changes of SLE. Include cytoid bodies, retinal hemorrhages, serous exudates or hemorrhages in the choroid, and optic neuritis. Exclude hypertensive, infectious, or drug causes.
8	Cranial nerve disorder	New onset of sensory or motor neuropathy involving cranial nerves.
8	Lupus headache	Severe, persistent headache. May be migrainous, but must be nonresponsive to narcotic analgesia.
8	CVA	New onset cerebrovascular accident(s). Exclude arteriosclerosis.
8	Vasculitis	Ulceration, gangrene, tender finger nodules, periungual infarction, splinter hemorrhages or biopsy, and angiogram proof of vasculitis.
4	Arthritis	≥2 joints with pain and signs of inflammation (i.e., tenderness, swelling, or effusion).
4	Myositis	Proximal muscle aching/weakness associated with elevated creatinine phosphokinase (CK)/aldolase or EMG changes or a biopsy showing myositis.
4	Urinary casts	Heme-granular or RBC casts.
4	Hematuria	>5 RBC/high-power field. Exclude stone, infection, or other cause.
4	Proteinuria	>0.5 gram/24 hours.
4	Pyuria	>5 WBC/high-power field. Exclude infection.
2	Rash	Inflammatory-type rash.
2	Alopecia	Abnormal, patchy, or diffuse loss of hair.
2	Mucosal ulcers	Oral or nasal ulcerations.
2	Pleurisy	Pleuritic chest pain with pleural rub or effusion, or pleural thickening.

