5.7. Table 7: Logistic Regression for Associated Factors with Renal Remission

	AOR	95% CI	p-value
Age	X.XXX	X.XXX - X.XXX	X.XXX
Gender (Female vs Male)	X.XXX	X.XXX - X.XXX	X.XXX
Treatment 1	ref		
Treatment 2	X.XXX	X.XXX - X.XXX	X.XXX
⋮	⋮	⋮	⋮
SLEDAI2K VALUE	X.XXX	X.XXX - X.XXX	X.XXX

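### Objective 2 uses the SLEDAI-2K value, which scores proteinuria, as a factor for proteinuria-defined renal remission; on the most natural reading of the timing, part of its odds ratio is built in

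*SAP*

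**What the plan says.** - **Outcome.** SAP 4.5.3 makes renal remission the dependent variable of univariate and multivariate logistic regressions. Protocol 3.2.2 gives the definition ("Renal remission: defined as proteinuria of" below 0.7 g/d or below 0.5 g/d, or at physician discretion).
- **Predictor.** Protocol 4.4.3 names disease activity as the clinical factor for this objective. The SAP Table 7 shell carries it as "SLEDAI2K VALUE".
- **Shared content.** In Protocol Appendix 2 the proteinuria item scores 4 points when proteinuria is ">0.5 gram/24 hours". Three other 4-point items are also renal: haematuria, pyuria and urinary casts ("Heme-granular or RBC casts").
- **Timing.** Protocol 4.4.3 says: "The variables included in the model will be taken from the measures closest to the time of enrolment". Protocol 3.3 aims for half the sample in remission and "50% of patients with no renal remission at the time of enrolment". SAP 4.5.3 names no visit. SAP Table 4 reports remission in six columns, from the prior 12 months to month 12, and nothing says which one feeds Table 7.
- **Selection.** Protocol 4.4.3 carries statistically significant factors into the multivariate model. SAP 4.5.3 screens at p≤0.25 and then keeps significant factors or confounders.
- **Score capture.** The retrospective list asks for the "Most recent total Systemic Lupus Erythematosus Disease Activity Index (SLEDAI), such as SLEDAI or SLEDAI-2K". Protocol section 5 makes recording of activity scales optional.

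**The concern.** If remission and SLEDAI-2K are read at about the same time, one proteinuria result can decide the outcome and also add 4 points to the predictor. The score would then be associated with remission even if no other aspect of disease activity were. Table 7 would show an odds ratio that a reader takes as the link between disease activity and remission, when some or all of it comes from the definitions. Neither screening rule protects against this, because a score that is significant through the shared item passes both.

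**Working it through.** **1. The plan's own figure.** The sample size for objective 2 reproduces. It uses a Wald test for one binary X with share B=0.35, P0=0.200, P1=0.385 and two-sided alpha 0.05. The overall P̄ = 0.65×0.200 + 0.35×0.385 = 0.265.

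N = [1.96·√(P̄(1−P̄)/B) + 0.842·√(P0(1−P0) + P1(1−P1)(1−B)/B)]² / [(P1−P0)²(1−B)] = (1.462+0.652)²/0.02225 ≈ 200.8, against 200 stated.

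The odds ratio is (0.385/0.615)/(0.200/0.800) = 2.504, against 2.508. The calculation is sound as arithmetic but does not address overlap between a predictor and the outcome.

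**2. Extent of the overlap, by remission rule.**
- Below 0.5 g/d, same assessment: everyone above 0.5 g/d is a non-remitter and carries the 4 points. Overlap is complete.
- Below 0.7 g/d: patients at 0.5 to 0.7 g/d are remitters who still score 4. Overlap is partial.
- Physician discretion, or score and remission dated differently: partial.

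**3. Size.** The documents give no score distribution, so these are assumptions: the other items are max(0, N(5, SD 3 to 5)), whose actual SD after truncation at zero is about 2.9 to 4.3; they are unrelated to remission; 50% are in remission; n=200; one predictor; the proteinuria item is always scored. The true odds ratio per point is 1.00.

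A hand approximation is log OR per point ≈ −d/v. Here d = 4(pN − pR), where pN and pR are the shares of non-remitters and remitters who score the item. Also v = s² + 16·½[pN(1−pN) + pR(1−pR)], with s = 2.9 or 4.3.

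| Remission rule | pR, pN | d | v | OR by hand | OR simulated | p<0.05 simulated |
|---|---|---|---|---|---|---|
| <0.5 g/d | 0, 1 | 4.00 | 8.41 to 18.49 | 0.62 to 0.81 | 0.62 to 0.81 | 100% |
| <0.7 g/d, 20% of patients at 0.5 to 0.7 | 0.40, 1 | 2.40 | 10.33 to 20.41 | 0.79 to 0.89 | 0.68 to 0.89 (5 to 20% in the band) | 95 to 100% |
| 30% discordant with the 0.5 rule | 0.30, 0.70 | 1.60 | 11.77 to 21.85 | 0.87 to 0.93 | 0.72 to 0.93 (10 to 30% discordant) | 65 to 100% |
| Both of the last two | 0.58, 0.82 | 0.96 | 11.54 to 21.62 | 0.92 to 0.96 | 0.92 to 0.96 | 29 to 50% |

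For the last row, pR = 0.7×0.40 + 0.3×1 and pN = 0.7×1 + 0.3×0.40. With 100 per group, z = 0.96/√(0.02·v) = 2.00 or 1.46. That gives p<0.05 in about 52% or 31% of trials, close to the simulation; repeat simulations put the lowest value at about 28%. With the proteinuria item removed, the odds ratio is 1.00 and rejection is about 3 to 6%.

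A separately built simulation (SD 3, 4 or 6; 35% or 50% in remission; cut-off 0.5 or 0.7; 0 or 30% of remission calls unrelated to proteinuria) gave 0.56 to 0.95 with 59 to 100% rejection, and 2 to 8% once the item was removed.

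**4. A later outcome visit.** Suppose later remission equals enrolment status with probability 0.5 or 0.7 and is otherwise random, under the 0.5 rule. The discordant share is then 25% or 15%. So d = 4×0.50 = 2.0 or 4×0.70 = 2.8, and v = s² + 16×0.25×0.75 = s² + 3.00 or s² + 16×0.15×0.85 = s² + 2.04. The odds ratio is 0.84 to 0.91 or 0.77 to 0.87. Simulation gave 0.77 to 0.91 overall, with about 87 to 100% rejection. Carried-over status therefore reproduces the concurrent result. With enrolment status in the model this disappears: within each status group under the 0.5 rule the item is constant, and the other items are unrelated by assumption.

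**The case against.** **The timing is not settled.** If the sentence on measures closest to enrolment covers the outcome too, the visit is in effect named. If it covers only predictors, the wording about attaining remission can mean a later visit. This stands, and a reader might infer that the odds ratio is certain to be circular. The documents do not support that: they lean towards enrolment without saying so, and overlap is complete only under one of three remission rules.

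**A later outcome cures it.** This is the opposite temptation, because baseline proteinuria is then a legitimate prognostic factor. It is true of proteinuria as such. But half the sample is to be recruited already in remission, so later remission is partly carried-over status, and the unadjusted total score again does not measure disease activity beyond proteinuria.

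**The total score is the intended activity measure.** The objective asks only about association and nowhere specifies activity independent of proteinuria. That is fair, and it is why the total score should still be reported. It does not make an odds ratio that partly reflects the outcome's own definition informative.

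**The sizes are assumed.** They are. With a skewed, non-negative score of true SD 5, rejection in the weakest case falls to about 23%, and to about 13% at an assumed n=120. All runs use a single predictor, while Table 7 reports adjusted odds ratios.

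**Limited reach.** Table 7 is a shell, SLEDAI capture is optional, and the primary objective is untouched. All true; this bears on weight, not on whether the overlap exists.

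**Item scores may not exist.** A reader might infer from the retrospective list that only totals are available. That list does ask for a total, but the prospective list and Appendix 1 do not say so, and Appendix 2 is an item-level form.

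**Conclusion.** The concern holds, conditional on timing. On the most natural reading of Protocol 3.3 and 4.4.3, predictor and outcome are read near enrolment and share the proteinuria result, and no passage removes the overlap. Under the stated assumptions the built-in odds ratio is about 0.62 to 0.96 per point, with p<0.05 in about 28 to 100% of runs, against 3 to 6% without the item. The direction is firm whenever the readings are concurrent; the size depends on the score distribution, the remission rule and the discordance, none of which the documents give. It does not follow that the rest of the Table 7 model or the sample size calculation is wrong. This should be corrected before the model is run; it affects one factor in one secondary objective.

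**What to change.** In Protocol 4.4.3, SAP 4.5.3 and Table 7:

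1. State the visit, and which of the documented remission definitions, supplies the dependent variable.
2. If it is concurrent with the predictors, enter SLEDAI-2K without the proteinuria item. Derive this from item-level scoring (the Appendix 2 form) or from confirmation that the item was scored at that assessment. Do not subtract 4 from every proteinuric patient's total: if the item was in fact unscored in 10 to 30% of them, that reverses the bias (odds ratio 1.02 to 1.13, p<0.05 in 10 to 74% of runs).
3. Report the total score and a score without any renal items as sensitivity analyses. The latter matters if discretion draws on other urinary findings. Assuming another 4-point renal item in 15 to 30% of patients, with remission withheld in 25 to 100% of those, the score without proteinuria alone still gave 0.84 to 0.99. The score without renal items gave 1.00, at the price of omitting part of disease activity.
4. If the outcome is at a later visit, keep the total score only with enrolment remission status in the model, or restrict to patients not in remission at enrolment.

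The cost is SAP and protocol wording, one derived variable and, where item scores are not already held, one field confirming that the item was scored. Because capture is optional and analysis is listwise, patients without item-level or confirmed scoring drop out of the adjusted-score analysis and must be counted. The documents do not show how many that would be. Restricting to non-remitters would leave about half the sample if the 50% recruitment target is met.

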5.8. Table 8: Changes in Quality of Life

Variable		Baseline visit	12 months	Change	p-value
SF36	Yes	n(%)	n(%)		
	No	n(%)	n(%)		
	mean±sd	XX.X±XX.X	XX.X±XX.X	XX.X±XX.X	0.XXX
	median (Q1-Q3)	XX.X (XX.X - XX.X)	XX.X (XX.X - XX.X)	XX.X (XX.X - XX.X)	
	Min-Max	XX.X - XX.X	XX.X - XX.X	XX.X - XX.X	
Physical functioning	mean±sd	XX.X±XX.X	XX.X±XX.X	XX.X±XX.X	0.XXX
Role limitation due to physical health	mean±sd	XX.X±XX.X	XX.X±XX.X	XX.X±XX.X	0.XXX
Role limitation due to emotional health	mean±sd	XX.X±XX.X	XX.X±XX.X	XX.X±XX.X	0.XXX
Energy/fatigue	mean±sd	XX.X±XX.X	XX.X±XX.X	XX.X±XX.X	0.XXX
Social functioning	mean±sd	XX.X±XX.X	XX.X±XX.X	XX.X±XX.X	0.XXX
Pain	mean±sd	XX.X±XX.X	XX.X±XX.X	XX.X±XX.X	0.XXX
General health	mean±sd	XX.X±XX.X	XX.X±XX.X	XX.X±XX.X	0.XXX
Emotional well-being	mean±sd	XX.X±XX.X	XX.X±XX.X	XX.X±XX.X	0.XXX

5.9. Table 9: Health Care Utility and Cost

Variable		Baseline visit 1	At 3 months	At 6 months	At 9 months	At 12 months	Overall
Number of office visits	mean±sd	XX.X±XX.X	XX.X±XX.X	XX.X±XX.X	XX.X±XX.X	XX.X±XX.X	XX.X±XX.X
	median (Q1-Q3)	XX.X (XX.X - XX.X)	XX.X (XX.X - XX.X)	XX.X (XX.X - XX.X)	XX.X (XX.X - XX.X)	XX.X (XX.X - XX.X)	XX.X (XX.X - XX.X)
	Min-Max	XX.X - XX.X	XX.X - XX.X	XX.X - XX.X	XX.X - XX.X	XX.X - XX.X	XX.X - XX.X
	Missing	XX	XX	XX	XX	XX	XX
Number of visits to other specialties for LN-related reasons	mean±sd	XX.X±XX.X	XX.X±XX.X	XX.X±XX.X	XX.X±XX.X	XX.X±XX.X	XX.X±XX.X
	median (Q1-Q3)	XX.X (XX.X - XX.X)	XX.X (XX.X - XX.X)	XX.X (XX.X - XX.X)	XX.X (XX.X - XX.X)	XX.X (XX.X - XX.X)	XX.X (XX.X - XX.X)
	Min-Max	XX.X - XX.X	XX.X - XX.X	XX.X - XX.X	XX.X - XX.X	XX.X - XX.X	XX.X - XX.X
	Missing	XX	XX	XX	XX	XX	XX
⋮	⋮	⋮	⋮	⋮	⋮	⋮	⋮
Cost (per patient)	mean±sd	XX.X±XX.X	XX.X±XX.X	XX.X±XX.X	XX.X±XX.X	XX.X±XX.X	XX.X±XX.X
	95% CI	(XX.X - XX.X)	(XX.X - XX.X)	(XX.X - XX.X)	(XX.X - XX.X)	(XX.X - XX.X)	(XX.X - XX.X)
	median (Q1-Q3)	XX.X (XX.X - XX.X)	XX.X (XX.X - XX.X)	XX.X (XX.X - XX.X)	XX.X (XX.X - XX.X)	XX.X (XX.X - XX.X)	XX.X (XX.X - XX.X)
	Min-Max	XX.X - XX.X	XX.X - XX.X	XX.X - XX.X	XX.X - XX.X	XX.X - XX.X	XX.X - XX.X
	Missing	XX	XX	XX	XX	XX	XX
Bahrain cost (per patient)	mean±sd	XX.X±XX.X	XX.X±XX.X	XX.X±XX.X	XX.X±XX.X	XX.X±XX.X	XX.X±XX.X
	95% CI	(XX.X - XX.X)	(XX.X - XX.X)	(XX.X - XX.X)	(XX.X - XX.X)	(XX.X - XX.X)	(XX.X - XX.X)
	median (Q1-Q3)	XX.X (XX.X - XX.X)	XX.X (XX.X - XX.X)	XX.X (XX.X - XX.X)	XX.X (XX.X - XX.X)	XX.X (XX.X - XX.X)	XX.X (XX.X - XX.X)
	Min-Max	XX.X - XX.X	XX.X - XX.X	XX.X - XX.X	XX.X - XX.X	XX.X - XX.X	XX.X - XX.X
	Missing	XX	XX	XX	XX	XX	XX
⋮	⋮	⋮	⋮	⋮	⋮	⋮	⋮
	mean±sd	XX.X±XX.X	XX.X±XX.X	XX.X±XX.X	XX.X±XX.X	XX.X±XX.X	XX.X±XX.X

	95% CI	(XX.X - XX.X)					
UAE cost (per patient)	median (Q1-Q3)	XX.X (XX.X - XX.X)					
	Min-Max	XX.X - XX.X					
	Missing	XX	XX	XX	XX	XX	XX

